[figure not shown]

1.4. Synopsis

Title of the clinical investigation	Performance and safety assessment of T4020 combined with standard post-operative therapy versus standard post-operative therapy in managing corneal epithelial defect following epi-off accelerated corneal crosslinking
International Coordinating Investigator	Prof (Associate) [name], Kayseri (Turkey)
Clinical investigation design	This is a prospective, randomised, double-masked, controlled, multicentre international clinical investigation
Clinical investigation objective(s)	
Primary objective: To assess performance of T4020 combined with standard post-operative therapy versus standard post-operative therapy regarding corneal epithelial defect (CED) healing following epi-off accelerated corneal crosslinking (CXL)
 
Other objectives: To assess ocular symptoms and safety

Clinical investigation endpoints	
Primary performance endpoint: Response defined as complete healing of CED (absence of CED) as assessed by the investigator on Corneal Fluorescein Staining (CFS) at slit lamp examination. (A patient with complete healing of CED could still present superficial punctate keratitis [SPK] or stained healing lines). Two time points will be considered: Day 3 (D3) and Day 4 (D4).
 
Secondary performance endpoint:
 
 - CED size assessed by the investigator on CFS at slit lamp examination after Contact Lens (CL) removal at D3, D4, and D5. 
Other performance endpoints:
 
 - Time to complete healing of CED. - Superficial punctate keratitis (SPK) (graded using the National Eye Institute [NEI] 0 - 15 scale) at D3, D4 and D5. - Presence or absence of stained typical healing lines at D3, D4 and D5. - Conjunctival staining (graded using the National Eye Institute [NEI] 0 - 18 scale) at screening visit and D5. - Total ocular pain score (graded on 0-10 Numeric Rating Scale) at D1, D2, D3, D4, and D5. - Each symptom including light sensitivity, burning / stinging, tearing, foreign body sensation (graded on 0-10 numeric rating scale: 0: absence of the symptom and 10: worst imaginable symptom) at D1, D2, D3, D4, and D5. - Sum of scores of light sensitivity, burning / stinging, tearing, foreign body

	
sensation at D1, D2, D3, D4 and D5.
 
 - Use of painkillers at D1, D2, D3, D4 and D5. - Measurement of the CED on CFS photos by a reading center at D1, D3, D4, and D5 (ancillary). 
Safety endpoints:
 
 - Conjunctival hyperaemia (graded using the McMonnies grading [0 to 5]) at D3, D4 and D5. - Uncorrected visual acuity (UCVA) and far best corrected visual acuity (BCVA) (using a Snellen chart) at screening visit and D5 after CL removal. - Non-contact intraocular pressure (IOP) at screening visit and D5 (after CL removal). - Adverse events (AEs)/ Adverse Device Effects (ADEs) recorded throughout the clinical investigation by the investigator.
Investigational Product	
T4020 will be combined with the standard post-operative therapy.
 
Dosing regimen: one administration into the CXL eye every other day for 5 days:
 
 • The first one at surgery before fitting CL, • The second one at D3 (after the visit, on the CL) at the site, • The third one at D5 (in the morning at home before the visit, on the CL). 
Saline solution will be combined with the standard post-operative therapy.
 
Dosing regimen: one administration into the CXL eye every other day for 5 days:
 
 • The first one at surgery before fitting CL, • The second one at D3 (after the visit, on the CL) at the site, • The third one at D5 (in the morning at home before the visit, on the CL).
Methodology	
Randomisation:
 
Patients will be randomised into two groups. In one group, T4020 will be used and, in the other group, saline solution will be used.
 
Auxiliary products and Therapies:
 
During the perioperative period, clinical investigation personnel will instil the drops. Then, the patients will instil the drops after they go home. All participants will be asked to use the same medications before and after the procedure as scheduled in the clinical investigation plan and detailed in the investigator manual:
 
In addition to cutaneous anti-infective solution and the bandage contact lens, the standardised treatment will include topical anaesthetic, direct-acting cholinergic agonist, topical antibiotic and artificial tears. Topical corticosteroid will be started after complete corneal healing.
 
Epi-off accelerated cross-linking with isotonic riboflavin will be performed as detailed in the protocol.
 
Patients will be permitted to take oral paracetamol 1g for ocular pain and

	paracetamol 500mg with codein 30mg or equivalent in case of severe pain.																									
Number of patients	About 147 screened patients to obtain 132 evaluable patients.																									
Inclusion criteria	
[1.1] Patient must provide signed and dated informed consent.
 
[1.2] Male or female patient at least 18 years of age.
 
[1.3] Patient with at least one eye:
 
 ○ with a progressive keratoconus (KC) occurring during the last 6 months according to the investigator judgement, ○ AND scheduled for an epi-off CXL procedure with no concomitant CXL in the other eye at the same time. 
[1.4] Corneal thickness $\geq 400 \mu\text{m}$ in the eye undergoing CXL.
 
[1.5] KC staging I-II according to Amsler-Krumeich classification in the eye undergoing CXL:
 
 
Keratoconus staging (using modified Krumeich's staging method)
 
  
 	Stage 1	Stage 2	Stage 3	Stage 4	
   
 Myopia/Astigmatism	< 5 D	5 - 8 D	8 - 10 D	Not measurable	
 
 K readings	< 48 D	48 - 53 D	53 - 55 D	> 55 D	
 
 Opaculessness	Vogt Streaks +-- No scars	Vogt Streaks +-- No scars	Vogt Streaks +++ No scars	Scars	
 
 Pachymetry	Normal ($>460 \mu\text{m}$)	400 μm - 460 μm	$>200 \mu\text{m}$	$<200 \mu\text{m}$	
  
  
		Stage 1	Stage 2	Stage 3	Stage 4	Myopia/Astigmatism	< 5 D	5 - 8 D	8 - 10 D	Not measurable	K readings	< 48 D	48 - 53 D	53 - 55 D	> 55 D	Opaculessness	Vogt Streaks +-- No scars	Vogt Streaks +-- No scars	Vogt Streaks +++ No scars	Scars	Pachymetry	Normal ($>460 \mu\text{m}$)	400 μm - 460 μm	$>200 \mu\text{m}$	$<200 \mu\text{m}$
	Stage 1	Stage 2	Stage 3	Stage 4																						
Myopia/Astigmatism	< 5 D	5 - 8 D	8 - 10 D	Not measurable																						
K readings	< 48 D	48 - 53 D	53 - 55 D	> 55 D																						
Opaculessness	Vogt Streaks +-- No scars	Vogt Streaks +-- No scars	Vogt Streaks +++ No scars	Scars																						
Pachymetry	Normal ($>460 \mu\text{m}$)	400 μm - 460 μm	$>200 \mu\text{m}$	$<200 \mu\text{m}$																						
Exclusion criteria	
2.1 Ophthalmic Exclusion Criteria:
 
in the eye undergoing CXL:
 
[2.1.1] Anesthetic / Hypoesthetic cornea $< 20 \text{ mm}$ with a Cochet-Bonnet aesthesiometer.
 
[2.1.2] Ocular surface disease index (OSDI) scores > 23.
 
[2.1.3] Schirmer test with anaesthesia $< 10 \text{ mm/5min}$.
 
[2.1.4] Tear Break-Up Time (TBUT) $< 7 \text{ sec}$.
 
[2.1.5] Corneal fluorescein staining score > 3 (NEI criteria).
 
[2.1.6] Conjunctival staining score > 3 (NEI criteria).
 
[2.1.7] Presence of any abnormalities preventing reliable measurements as judged by the investigator.
 
[2.1.8] History of any ocular injury.
 
[2.1.9] History within 1 month before the screening visit or any active ocular infection (e.g., bacterial, viral, fungal, acanthamoeba), ocular injury, and associated corneal ulceration and abscess, occurring during the screening period.
 
at least in one eye:
 
[2.1.10] History of any atopic keratoconjunctivitis (AKC), any active uveitis, or any other ocular disorder or condition that could be in the judgment of the investigator, jeopardize patient safety or interfere with the
																									

	
interpretation of clinical investigation results.
 
[2.1.11] No active vernal keratoconjunctivitis (VKC) within 6 months including D1.
 
[2.1.12] Ocular hypertension or glaucoma requiring an ophthalmic medicinal product.
 
[2.1.13] History of ocular Herpes.
 
[2.1.14] Far BCVA \leq 2/10 Snellen.
 
[2.1.15] Abnormal eye lid anatomy, blinking, or naso-lachrymal drainage system.

	
2.2 Systemic/non-ophthalmic exclusion criteria
 
[2.2.1] Known or suspected hypersensitivity to one of the components of:
 
 - the investigational products and/or heparinoids or heparin or - the auxiliary products: 
ofloxacin and other quinolones (eg ciprofloxacin, norfloxacin, moxifloxacin, levofloxacin), dexamethasone, povidone and iodine povidone, oxybuprocain and other local anaesthetics, cholinergic agonists, riboflavin and others chemical related substances, paracetamol, other ingredients of the mentioned medicinal products or medical devices,
 
 - the materials and medicinal products or medical devices used during standard ophtalmological examinations.
	
[2.2.2] Any condition judged by the investigator to be incompatible with the clinical investigation or likely to interfere with the clinical investigation results e.g.: acute or chronic severe disease (hepatic, renal, endocrine, neoplastic, haematological disorder, immunosuppression, infectious diseases, severe psychiatric illness, relevant cardiovascular abnormalities, etc) and/or any other factor or abnormality.

	
[2.2.3] On-going malignancy during the screening period or history of malignancy within 5 years before D1.

	
[2.2.4] Any history of known clinically significant conditions:
 
 i. Graft-versus-host disease, transplanted patient. ii. Any other non-controlled systemic disorder. iii. History of drug addiction or alcohol abuse.
	
2.3 Specific exclusion criteria for women:
 
[2.3.1] Pregnancy or lactation.
 
[2.3.2] Childbearing potential woman who is not using a reliable method of contraception (oral contraceptive, intra-uterine device, subcutaneous contraceptive implant, vaginal ring, patch) or is not surgically sterilised.

	
2.4 Exclusion criteria related to general conditions:
 
[2.4.1] Inability of patient and/or relatives to understand the clinical investigation procedures and thus inability to give informed consent.
 
[2.4.2] Non-compliant patient and/or relatives (e.g. not willing to attend a visit, way of life interfering with compliance).

[2.4.3]	Participation in the present clinical investigation at the same time as another clinical investigation.					
[2.4.4]	Participation in this clinical investigation within 4 weeks after the end of a previous clinical investigation (or within 5 half-life of the previously tested product if longer than 4 weeks).					
[2.4.5]	Patient previously randomised in this clinical investigation.					
[2.4.6]	Patient being institutionalised because of legal or regulatory order, inmate of psychiatric wards, prison or state institutions, or employee of the clinical investigation sites or of the Sponsor's company.					
[2.4.7]	Patient not covered by the government health care scheme when existing in the concerned country.					

2.5 Exclusion Criteria Related to Previous and Concomitant Treatments (Medications / non-medicinal therapies / procedures):

Ocular surgery or topical treatment concerned only eye undergoing CXL						
Before inclusion						After inclusion D1 to D5
At any time	3 Years	1 Year	6 Months	1 Month	1 Week	Product period
Corneal graft or corneal rings						
Corneal refractive surgery (e.g., LASIK, LASEK, PRK) or anticipated during the clinical investigation						
Intravitreal injection						
Previous corneal crosslinking						
Systemic or topical calcineurin inhibitors (e.g. Restasis®, Ikervis®, pharmacy made formulations) or other non-steroidal immunosuppressive treatments						
Amniotic membrane graft						
Isotretinoïn						
Other ocular surgery (e.g., palpebral and cataract surgery)						
Permanent punctal plugs (with the exception of semi-permanent or temporary plugs with a prohibition period of 3 months)						
Other laser procedures						
Systemic or topical non-steroidal anti-inflammatory drugs (NSAIDs), corticosteroids (except the standardised post-operative topical corticosteroid – please refer to the investigator)						

	
All randomised patients having received at least one dose of investigational product and with at least one post-baseline performance assessment on product.
 
Per protocol (PP) set: All mITT patients without any major clinical investigation plan violation.
 
Safety endpoints will be analysed in the safety set. Performance endpoints will be primarily analysed in the mITT set.
 
Baseline: The baseline visit is the inclusion visit (D1) for all assessments.
 
Sample size: The principal statistical hypothesis is the superiority of T4020 compared to control for the primary efficacy variable. The sample size determination is based on the primary efficacy endpoint, i.e. the response defined as complete healing of CED (absence of CED) in the eye undergoing CXL as assessed by the investigator on Corneal Fluorescein Staining (CFS) at slit lamp examination at Day 3 (D3) and Day 4 (D4) using the Hochberg procedure for multiple testing. Using this step-up procedure, unadjusted p-values are ordered from the largest (p1) to the smallest (p2). If the largest p-value (p1) is lower than 0.05, both null hypotheses can be rejected at the overall 5%-level of significance. If the largest p-value (p1) is greater than 0.05 and the smallest p-value (p2) lower than 0.025, only the null hypothesis corresponding to p2 can be rejected at the overall 5%-level of significance. Bases on estimated response rates of 60% in the T4020 group and 30% in the control group, 132 evaluable patients (66 per group) are needed to achieve at least 90% power using a two-sided 0.025 significant nominal level.
 
Interim analysis: No interim analysis is planned.

Planned schedule	
Planned initiation of the clinical investigation: September 2016 Planned completion date of the clinical investigation: June 2017

FLOW CHART: Clinical investigations are to be conducted as per the following schedule of investigation procedures:

Clinical investigation procedure	Screening Within 60 Days [D] before D1	Visit D1				Visit D2 = 24h (± 2h) ^(a)	Visit D3 = 48h (± 2h)	Visit D4 = 72h (± 2h)	Final Visit D5 = 96h (± 2h) ⁽ⁿ⁾
		Pre-op.	Intra-op.	Post-op.	Phone call 4 hours post- op. ^(a)				
Informed consent	X								
Demography / Smoking status	X								
Keratoconus (KC) history	X								
Ocular medical and surgical history	X								
Ocular surface disease index (OSDI)	X								X
Systemic medical and surgical history	X								
Verification of inclusion and exclusion criteria	X	X							
Previous and concomitant ocular/non ocular products	X	X				X	X	X	X
Patient diary :									
- Painkiller(s) use ^(b)		X ^(c)		X	X	X	X	X	X
- Ocular pain assessment (Numeric Rating Scale, NRS)	X ^(c)	X ^(c)		X	X ^(d)	X ^(e)	X ^(e)	X ^(e)	X ^(e)
Ocular symptoms ^(f)					X	X	X	X	X
Corneal topography with pachymetry	X								
Far Uncorrected and Best Corrected Visual acuity (UCVA and BCVA) with manifest refraction	X								X
Slit-lamp examination ^(g)	X	X					X	X	X
Tear Break-up time (TBUT) with fluorescein	X								
Corneal fluorescein staining with CED assessment and photos (blue light) ^(h)	X						X	X	X
Conjunctival staining with lissamine green	X								X
Conjunctival hyperaemia							X	X	X
Corneal sensitivity assessment (by the Cochet-Bonnet aesthesiometer)	X								
Peri-operative pachymetry			X						

Clinical investigation procedure	Screening Within 60 Days [D] before D1	Visit D1				Visit D2= 24h ($\pm 2h$) ^(a)	Visit D3 = 48h ($\pm 2h$)	Visit D4 = 72h ($\pm 2h$)	Final Visit D5 = 96h ($\pm 2h$) ^(o)
		Pre-op.	Intra-op.	Post-op.	Phone call 4 hours post- op. ^(a)				
Intraocular pressure (IOP) measurement on both eyes (non-contact tonometry)	X								X ⁽ⁱ⁾
Schirmer test with anaesthesia	X								
Surgery: epi-off corneal collagen cross-linking (CXL) procedure			X						
Randomisation		X							
Investigational product instillation			X ^(j)				X ^(k)		X ^(l)
Contact lens (CL) insertion ^(m)			X				X	X	
Peri-operative photos				X					
Urinary pregnancy test ⁽ⁿ⁾	X								
Adverse Event(s) (AE) / Adverse Device Effect(s) (ADEs) collection		X	X	X	X	X	X	X	X

^(a) A phone call will be performed 4 hours after the CXL procedure by the investigator/delegate to collect the ocular symptoms and to remind the patient to complete the diary. Visit D2 will be also a phone call done by the investigator/delegate.

^(b) Number of painkiller(s) pills recorded by the patient in the patient diary will be collected. The 1st administration of the painkiller (Paracetamol 1g) will be done 1 hour after CXL. The 2nd administration will be at least 4 hours later and no more than 4 times daily. In case of real severe pain, patient can take Paracetamol 500mg with 30mg Codein instead of Paracetamol 1g, not exceeding 4 tablets/day (including tablets with paracetamol and tablets with paracetamol/codein).

^(c) For training purposes.

^(d) The patient should be instructed to note the NRS pain score 1 hour after CXL procedure before the 1st painkiller administration, then 3, 6 and 12 hours after CXL procedure and before painkiller administration.

^(e) The patient should be instructed to note the NRS pain score at wake up time(8:00 am +/- 2h), midday (2:00 pm +/- 2h) and bedtime (8:00 pm +/- 2h) and before painkiller administration.

^(f) Ocular symptoms (light sensitivity, burning/stinging, tearing, foreign body sensation) will be collected by the investigator/delegate.

^(g) Slit lamp examination: any clinically relevant finding will be recorded.

^(h) The CED will be measured with caliper / with the slit lamp after contact lens (CL) removal if applicable.

⁽ⁱ⁾ IOP at visit D5 if complete healing.

^(j) The investigational product will be instilled by the medical staff before CL insertion at the end of the CXL procedure at visit D1.

^(k) The investigational product will be instilled by the medical staff after CL insertion at Visit D3.

^(l) The investigational product will be instilled by the patient (on the CL) in the morning D5 before the Visit.

^(m) The removal of the CL will be done with forceps after hydration before ocular examination and a new CL will be used at visit D3 and visit D4.

⁽ⁿ⁾ Women of child bearing potential must have a negative urinary pregnancy test prior to the initial instillation of investigational product.

^(o) Follow up of the patient can be done if complete healing isn't reached, according to the investigator judgement. All procedures will be performed as scheduled for the final visit D5.

Op.: Operatively

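### Does the reading-centre measurement of the epithelial defect at D1 lack a scheduled image?

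*Combined protocol and SAP*

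**What the plan says.** Section 1.4 (Synopsis), other performance endpoints, includes "Measurement of the CED on CFS photos by a reading center at D1, D3, D4, and D5 (ancillary"). The secondary endpoint is the investigator's own measurement, which starts later: "CED size assessed by the investigator on CFS at slit lamp examination after Contact Lens (CL) removal at D3, D4, and D5".

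The Flow Chart has two rows that concern photographs:

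- "Corneal fluorescein staining with CED assessment and photos (blue light"), marked at Screening, D3, D4 and D5. All four D1 sub-columns and D2 are blank.
- "Peri-operative photos", marked once, in the D1 post-operative column. The row has no footnote and states no stain, light or lens status.

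Other entries bear on D1. The row "Contact lens (CL) insertion" is marked intra-operatively at D1 and again at D3 and D4. The row "Slit-lamp examination" has its only D1 mark before surgery. Footnote (a) adds: "Visit D2 will be also a phone call done by the investigator/delegate". The Synopsis also makes D1 the baseline visit for all assessments.

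**The concern.** Read literally, the endpoint list asks for a fluorescein image at D1 and the schedule does not provide one. A site working only from the chart might take an unstained or white-light photograph after surgery, or take it through the bandage lens, and the reading centre might be unable to outline the defect.

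The image could not be retaken. No in-person examination is charted between the end of surgery and D3, at 48 hours, by which time many eyes should have healed. The screening image precedes epithelial removal, and the investigator's measurement begins at D3. In the text available, the D1 photograph is therefore the only possible record of starting defect size. If it failed, the ancillary D1 reading would be lost, and with it a descriptive check that the arms began with defects of similar size.

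**Working it through.** **1. The plan's own figure.** The Synopsis (sample size) gives 66 per group for "estimated response rates of 60% in the T4020 group and 30% in the control group", 90% power and a two-sided level of 0.025. With pooled variance under the null:

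n = [z(0.9875)·√(2·0.45·0.55) + z(0.90)·√(0.60·0.40 + 0.30·0.70)]² / (0.60 − 0.30)²

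= [2.2414·0.7036 + 1.2816·0.6708]² / 0.09 = (1.577 + 0.860)² / 0.09 ≈ 66 per group, 132 in total, power 0.900.

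The figure reproduces. Its inputs are healing proportions, and no D1 area enters.

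**2. The entries side by side.**

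| Item | Time points |
|---|---|
| Reading-centre measurement (Synopsis) | D1, D3, D4, D5 |
| Fluorescein and blue-light photo row (Flow Chart) | Screening, D3, D4, D5 |
| Peri-operative photo row (Flow Chart) | D1 post-op |
| Union of the two photo rows | Screening, D1, D3, D4, D5 |

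Together the two photo rows cover every reading-centre time point. The mismatch is in how the D1 photograph is described; a D1 photograph is charted.

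**3. Can lens status be inferred from the columns?** Lens insertion is marked intra-operatively and the photograph post-operatively, which might suggest a photograph through the lens. The D1 sub-columns are not a strict time sequence, however. Footnote (d), attached to the column for the call 4 hours after surgery, covers pain scores at 1, 3, 6 and 12 hours. Footnote (m) says in general that the lens comes out before the eye is examined. The order of lens and photograph is left open, and neither reading can be built on.

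**4. Size of the exposure.** Planned readings are 132 patients × 4 time points = 528, and the D1 share is 132/528 = 25%. If a share f of patients had no measurable D1 image, the loss would be 132·f. The documents do not give f, so the values below are assumptions:

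| f (assumed) | D1 readings lost |
|---|---|
| 0% | 0 |
| 10% | 13 |
| 25% | 33 |
| 50% | 66 |
| 100% | 132 |

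The last row requires the charted photograph to be unusable at every site.

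**5. Could D3 stand in for D1?** No. If the planning rates hold at D3, 66·0.60 + 66·0.30 = 39.6 + 19.8 = 59.4 of 132 eyes (45%) already have a defect size of zero. This shows why a D1 image is useful. It does not show that the image will be missing.

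**6. What depends on the D1 area?** The primary endpoint is the presence or absence of a defect at D3 and D4. The secondary endpoint is the investigator's size at D3, D4 and D5. Neither is defined as a change from D1, and no visible passage plans an analysis adjusted for D1 area. Randomisation is charted before surgery and the trial is double-masked. Starting size is therefore balanced in expectation, and with masking intact the surgeon cannot fit the removed area to the allocation.

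**The case for a change.** The best case for acting is that the remedy is one footnote, while a missed image is irrecoverable. Sites in a multicentre international trial may differ in how they take an unspecified photograph. D1 is the stated baseline, and the footnote about measuring after lens removal is attached only to the fluorescein row. Even if the imaging procedure is set out elsewhere, the chart still fails to show the D1 fluorescein image that the endpoint list implies.

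Part of this stands. The link between the two entries is not written down, and a clarifying line would do no harm.

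It does not amount to a flaw in the plan. The text available is a synopsis and a schedule; the Synopsis (methodology) refers to the protocol for the crosslinking procedure and to an investigator manual for the medication details. Stain, light and lens conditions belong in such text, and their absence from a one-line chart row does not show that they are undefined. Nor does a schedule mismatch create a need for a supportive analysis adjusted for D1 area. Such an analysis would gain little precision if the removed area is standardised, and it would not change the conclusion on the primary endpoint.

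**Conclusion.** The discrepancy is real but amounts to a missing cross-reference for an ancillary endpoint. A D1 photograph is scheduled, and the sensible reading is that it is the one sent to the reading centre. An analyst would use the D1 readings that can be measured, report the number missing by arm, and analyse the investigator's D3 to D5 sizes as planned.

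The effect on the primary comparison, the secondary comparison and the sample size is nil. The exposure is between 0 and 132 of 528 ancillary readings, and nothing in the documents places it within that range. The conclusion assumes that the peri-operative photograph is the intended D1 image. If it is not, the trial loses one ancillary time point and a descriptive balance check, and the main results remain sound. It also assumes that no unseen part of the analysis plan makes D1 area an input to the primary or secondary analysis. No change to the plan is called for.

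### No adjustment for starting defect area is specified for the D3/D4 healing or CED-size comparisons, although a D1 reading-centre measurement is listed and D1 is defined as baseline

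*Combined protocol and SAP*

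**What the plan says.** All references are to section 1.4, Synopsis, and the flow chart that follows it.

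- **Primary endpoint:** "Response defined as complete healing of CED (absence of CED) as assessed by the investigator on Corneal Fluorescein Staining (CFS) at slit lamp examination". D3 and D4 are both tested, under a Hochberg rule.
- **Secondary endpoint:** "CED size assessed by the investigator on CFS at slit lamp examination after Contact Lens (CL) removal at D3, D4, and D5". The investigator records no D1 size, so this endpoint has no starting value of its own.
- **Other performance endpoints, last item:** "Measurement of the CED on CFS photos by a reading center at D1, D3, D4, and D5 (ancillary"). This is the only D1 defect measurement named.
- **Baseline:** "The baseline visit is the inclusion visit (D1) for all assessments".
- **Sample size:** "Bases on estimated response rates of 60% in the T4020 group and 30% in the control group", giving 132 evaluable patients (66 per group) at two-sided 0.025. No covariate enters.
- **Flow chart:** the row "Corneal fluorescein staining with CED assessment and photos (blue light") is marked at screening, D3, D4 and D5, with no mark under D1. The D1 imaging is a separate row, "Peri-operative photos", with one mark that appears to fall in the post-operative column. Randomisation is marked pre-operatively. Footnote (j) puts the first instillation at the end of the procedure, before the contact lens is inserted.

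The available text names no test, model, covariate or stratification factor for healing or CED size.

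**The concern.** The surgeon creates the defect, and the primary endpoint asks whether it has closed by 48 or 72 hours. It is reasonable to expect a larger starting wound to be less likely to have closed by a fixed time, and to leave a larger residual area. The documents give no figure for this. The trial is multicentre and international, so the area removed may vary between surgeons.

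If starting area does predict closure and is left out of the analysis, its variation stays in the error term and a chance difference between arms moves the estimate. The plan lists the measurement and calls D1 baseline, yet places the value among the outcomes. Naming the covariate in advance also removes the temptation to decide on adjustment after an imbalance has been seen.

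**Working it through.** **1. The plan's own figure.** Inputs from the sample-size paragraph: 60% v 30%, two-sided 0.025, 90% power. Pooled-variance formula without continuity correction, mean rate 0.45:

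n = [2.2414 × √(2 × 0.45 × 0.55) + 1.2816 × √(0.6 × 0.4 + 0.3 × 0.7)]² / 0.30² = [1.577 + 0.860]² / 0.09 = 65.97, so 66 per group.

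Power at 66 per group is 90.0% by this approximation and 90.9% by exact enumeration of the chi-square test. The stated size is right and uses no covariate.

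**2. Chance imbalance in D1 area.** The SE of the difference in standardised means is √(2/66) = 0.174 SD. Multiplied by 1.96, this is 0.34 SD, so about 1 trial in 20 has an imbalance of at least that size.

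**3. What such an imbalance does to the response difference** (association assumed):

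- Logistic scale, 30% healing rate: 2.8, 4.5 and 6.4 points for odds ratios of non-healing of 1.5, 2 and 3 per SD.
- Latent-normal scale, mean rate 45%: 0.396 × r × 0.34 gives about 4 points at r = 0.3 and about 7 at r = 0.5.

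For scale, the planned difference is 30 points and its unadjusted SE is √(0.24/66 + 0.21/66) = 8.3 points. That SE already allows for chance imbalance of this kind.

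**4. Power for healing.** Simulation with 3,000 trials per row, 66 per group, marginal rates held at 60% and 30%, two-sided 0.025. The unadjusted test is chi-square. The adjusted test is a logistic likelihood-ratio test with D1 area.

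| Assumed odds ratio per SD | Unadjusted | Adjusted | Gain (points) |
|---|---|---|---|
| 1.0 | 90.2% | 89.6% | −0.6 |
| 1.5 | 90.9% | 91.7% | 0.8 |
| 2.0 | 91.2% | 93.3% | 2.1 |
| 3.0 | 90.9% | 95.1% | 4.2 |

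The simulation error of each power figure is √(0.9 × 0.1/3000) = 0.5 point. With equal 30% rates, the rejection rate was 2.1 to 2.9% unadjusted and 2.0 to 3.2% adjusted, with simulation error √(0.025 × 0.975/3000) = 0.3 point. Adjustment therefore made little difference to the error rate.

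**5. CED size.** With a continuous outcome and correlation r, ANCOVA multiplies the residual variance by 1 − r²:

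- r = 0.3: 0.91, so 132 patients act like 132/0.91 = 145.
- r = 0.5: 0.75, so 132 patients act like 132/0.75 = 176.

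These are upper figures, because healed eyes have size zero. Take a latent normal size with unit variance floored at zero, a proportion h healed, and latent correlation ρ with D1 area. The observed r² is then ρ²(1 − h)²/V, where V is the variance of the floored outcome.

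| Healed, h | V | (1 − h)²/V | r² for ρ = 0.3 to 0.5 |
|---|---|---|---|
| 30% | 0.564 | 0.49/0.564 = 0.87 | 8 to 22% |
| 60% | 0.247 | 0.16/0.247 = 0.65 | 6 to 16% |
| 80% (assumed for D5) | 0.0936 | 0.04/0.0936 = 0.43 | 4 to 11% |

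**The case against.** **The text is incomplete.** Only the synopsis and flow chart are available, and the statistical part begins partway through the analysis-set definitions. A reader might infer that the comparisons will be unadjusted. The documents do not support that: no model is given for any endpoint, and ancillary status does not rule out use as a covariate. What stands is that no adjustment is specified in the available text.

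**Starting area may matter little.** A reader might also take it as the main determinant of closure. No figure in the documents supports this. The procedure is said to be detailed in the protocol. If the size of the removed area is standardised there, its variation shrinks and the gain may vanish. The secondary endpoint is a slit-lamp caliper measurement while the covariate would come from photos, which may weaken the correlation further. All of this stands, and is why the gain is given as a range that includes zero.

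**The D1 value may not exist in usable form.** The endpoint list plans a D1 reading of fluorescein photos, but the flow chart marks none. This stands. It makes the adjustment conditional on reconciling the two places, and the planned D1 reading needs that reconciliation in any case.

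**D1 area may not be a clean baseline.** The defect is made after randomisation, and the photo's timing relative to the first instillation is not stated. In a double-masked trial, with the photo taken in the same surgical session, a treatment effect on the measured area is hardly plausible. The timing should still be written down.

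**Nothing is invalid without adjustment.** Correct: a shift of 3 to 7 points from a 1-in-20 imbalance lies within one unadjusted SE of 8.3.

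**Conclusion.** The point holds as a forgone precision gain. It is not a bias, and the sample size is not wrong.

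For healing, the gain is about 1 to 4 points of power for assumed odds ratios of 1.5 to 3 per SD. For CED size, the variance reduction is at most 9 to 25% for assumed correlations of 0.3 to 0.5, and about 6 to 16% where 60% of eyes have healed. With no association, the simulated cost for healing is 0.6 point, close to simulation error.

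The result rests on three conditions: the association is of the assumed size, a usable D1 reading exists, and treatment cannot have affected that reading. Because the possible gain clearly exceeds the possible loss, the adjustment is worth specifying before unmasking.

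**What to change.** 1. **CED size at D3, D4 and D5:** pre-specify ANCOVA with arm and reading-centre D1 CED area. Because many eyes will have size zero, add a check of the model or a robust or rank-based alternative.
2. **Response at D3 and D4:** pre-specify a logistic model with arm and D1 area, reported as a standardised risk difference. Leave the Hochberg rule unchanged.
3. **Sensitivity:** keep the unadjusted comparison.
4. **Unreadable or missing D1 photo:** impute the overall mean, so that no patient is dropped.
5. **Reporting:** show D1 area in the baseline table, not as an outcome.
6. **Documents:** reconcile the D1 photo reading in the endpoint list with the flow chart. State whether the peri-operative photo is the one that is read, whether it is stained, and when it is taken relative to the first instillation.

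Cost: analysis wording and a clarification of the schedule, with no extra patients or visits. If the reconciliation shows that no usable D1 photo is taken, items 1, 2, 4 and 5 cannot be carried out as written, and the planned D1 reading cannot be delivered either.
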